## 5.8 Discontinuation from the Treatment/Study

Subjects will be removed from the study treatment at any time if they meet any of the following criteria:

- Documented radiographic or clinical progression of disease\*
- Noncompliance with any part of the study, as evaluated by the Investigator and Medical Monitor
- Clinically unacceptable toxicities despite optimal treatment or dose reduction
- Withdrawal of consent
- Investigator's decision (in agreement with the Sponsor/Medical Monitor or designee)
- Lost to Follow-up
- Death

\* Subjects may remain on treatment if, in the opinion of the Investigator and with the agreement of ArQule's Medical Monitor, they continue to derive benefit from the treatment.

Subjects will be removed from the study if they meet any of the following criteria:

- Safety follow-up visit is completed per protocol and drug-related AEs have resolved to baseline, CTCAE Grade 1, stabilized, or are deemed irreversible.
- Withdrawal of consent
- Lost to Follow-up
- Death

## 5.9 Study Discontinuation

The Sponsor reserves the right to temporarily or permanently discontinue the study at any site and at any time. Reasons for study discontinuation may include, but are not limited to, the following:

- Safety concerns
- Poor enrollment
- Non-compliance with the protocol, Good Clinical Practice (GCP) guidelines, or other regulatory requirements by the Investigator(s)
- Request to discontinue the trial by a regulatory or health authority
- Discontinuation of product development
- Manufacturing difficulties/concerns

The Sponsor and/or designee will promptly inform all Investigators and the appropriate regulatory authorities if the study is suspended or terminated for safety reasons. In the case of such termination, the Investigator will notify the Institutional Review Board (IRB) or Independent Ethics Committee (IEC).

## 6 STUDY PROCEDURES

### 6.1 Medical History

Medical history will include but not be limited to the following:

- Demography: date of birth, sex, ethnic origin, height, and weight
- Clinically significant prior diagnoses, surgeries, and current medications
  - Medications used within 30 days prior to the first dose of ARQ 087 should be reported
- Prior cancer history, current cancer diagnosis, tumor stage at time of diagnosis and screening, previous anti-cancer therapy, including dates, duration and outcome of treatment, previous radiation therapy, including anatomic site, dose and dates of treatment, previous cancer-related surgical procedures, including type of the procedure and dates

### 6.2 Physical Examination

Complete physical examination of the major body systems, including mucous membranes, skin, height (Baseline visit only), weight (Baseline visit, Cycle 1 Day 1 and Day 15, on Day 1 of all subsequent cycles, and End of Treatment visit), vital signs (blood pressure, heart rate, respiratory rate, temperature [oral, axillary, or tympanic]), and ECOG PS (Appendix 2).

### 6.3 12-Lead ECG, Echocardiography, and MUGA Scan

Twelve-lead ECG should be conducted at the Baseline Visit, on Day 1 and Day 15 of Cycle 1, on Day 1 of all subsequent cycles (e.g., Cycle 2, Cycle 3, etc.), and at the End of Treatment Visit. Additional ECG(s) may be conducted if clinically indicated.

For subjects previously treated with anthracyclines (e.g., epirubicin [Ellence, Pharmorubicin]; idarubicin [Idamycin]; doxorubicin [Adriamycin, Rubex]; and daunorubicin [Cerubidine]), an echocardiography or MUGA scan to measure LVEF should be performed at Baseline, and, if clinically indicated, every eight/twelve weeks (e.g., Day 1 Cycle 3, Day 1 Cycle 6, Day 1 Cycle 9, Day 1 Cycle 12, etc.), and at the End of Treatment Visit.

For the individual subject, the same method of measuring LVEF should be used throughout the study.

### 6.4 Clinical Laboratory Tests

Safety laboratory determinations will include hematology, blood chemistry, liver function tests, coagulation tests, and urinalyses. All laboratory tests required during the study must be obtained at a local laboratory designated by the Investigator. Fasting clinical blood tests obtained during the Pre-study Visit can be used for Day 1 if they are performed within 72 hours prior to the first dose of the study drug (Treatment Period 1, Day 1 in Cohorts 1-4 or Cycle 1 Day 1 visit in Cohort 5 and all subsequent cohorts). During Treatment Period 2 (Cohorts 1-4) or the Continuous Treatment Administration (Cohort 5 and all subsequent cohorts), clinical blood tests can be obtained within 24 hours prior to the scheduled visit.

Chemistry samples should be taken in a fasting state (fasting at least 8 hours) prior to administration of the morning dose of ARQ 087\*.

- Hematology: complete blood count (CBC) including hemoglobin, hematocrit, white blood cell count (WBC) with 5-part differential, red blood cell (RBC), platelet, and reticulocyte count
- Blood chemistry: albumin, bicarbonate, blood urea nitrogen (BUN), calcium, chloride, creatinine, glucose, glycated hemoglobin (HbA1c)\*\*, magnesium, phosphate, potassium, total protein, sodium, uric acid
- Liver function tests (LFT): alanine transaminase (ALT), aspartate transaminase (AST), alkaline phosphatase (ALP), total and direct bilirubin, lactate dehydrogenase (LDH)
- Thyroid function tests (at Baseline and End of Treatment, and if clinically indicated): thyroid stimulating hormone (TSH), triiodothyronine (total T3), thyroxine (free T4)
- Coagulation tests (at Baseline and End of Treatment, and if clinically indicated): prothrombin time (PT), international normalized ratio (INR), and partial prothrombin time (PTT)
- Routine urinalysis: dipstick and microscopy (only if clinically indicated or dipstick is not done) including protein, specific gravity, glucose and blood
  - To assess ARQ 087 metabolism, the Sponsor may request collection of 24-hour urine samples
- Serum pregnancy test (at Baseline and End of Treatment only): for female subjects of childbearing potential

\*ARQ 087 should be administered in the fasted state, except to subjects enrolled in the Food-effect Cohort.

\*\*HbA1c should be done at Baseline and End of Treatment, and if clinically indicated

## 6.5 Pharmacokinetic Assessments

Pharmacokinetic variables will include  $C_{max}$ , AUC, and half-life. To assess single dose PK, blood samples will be collected for four consecutive days during Treatment Period 1 (Cohorts 1-4), on Day 1 (full assessment), Day 2 (24 hrs post-dose), Day 3 (48 hrs post-dose), and Day 4 (72 hrs post-dose). The washout period between Treatment Period 1, Day 1 and Treatment Period 2, Day 1 Cycle 1 should be at least 72 hours. During Treatment Period 2 (continuous administration of ARQ 087), PK samples will be collected on Day 8, Day 15, Day 22 (full assessment), and Day 23 (24 hrs post-dose on Day 22) of Cycle 1 (see Appendix 3). However, for subjects enrolled in **Cohort 1** (25 mg every other day), Cycle 1 Week 4 visits should be scheduled on the day of ARQ 087 administration and the next consecutive day, when drug is not taken, e.g., Cycle 1 Day 21 and Day 22 or Cycle 1 Day 23 and Day 24. Also, a Cycle 1 Day 1 pre-dose sample should be collected if the Cycle 1 Day 1 visit differs from the Treatment Period 1, Day 4 visit (72 hours).

During continuous administration of ARQ 087 (Cohort 5 and all subsequent cohorts, including ALL subjects enrolled in the Food-effect Cohort, and for up to 10 subjects enrolled in the Expanded Cohort at selected sites), PK samples will be collected on Day 1 (full assessment), Day 2, Day 8 (pre-dose), Day 15 (pre-dose), Day 22 (full assessment), and

Day 23 (pre-dose) of Cycle 1; and on Day 1 and Day 15 of all subsequent cycles (pre-dose), and End of Treatment (see Appendix 3).

The blood sampling date and time and the time of the last dose of ARQ 087 administration prior to PK blood draw should be recorded on the eCRF.

Detailed instructions for collection and shipment of plasma PK samples will be provided in the laboratory manual.

## 6.6 Pharmacodynamic Assessments

The goal of the proposed biomarker study is to evaluate the tumoral and serum- or plasma-based pharmacodynamic response in subjects treated with ARQ 087.

Information on tumor FGFR protein expression, gene copy number and mRNA amplification, and/or mutational/gene re-arrangement (fusion, translocation) status is required for this study. If these are not known, tumor biopsy should be done to assess these parameters prior to the first dose of ARQ 087. All baseline samples (archival or newly acquired) will be evaluated by immunohistochemistry (IHC), FISH (gene copy number), ISH or qNPA (mRNA amplification), and/or DNA sequencing (mutational/gene re-arrangement [fusion, translocation] status assessment).

Pathology specimens (pre- and post-treatment tumor biopsies) will be evaluated for changes in total FGFR1, total FGFR2, pFGFR, pFRS2 $\alpha$ , and/or pERK status by either IHC, mesoscale, or immunoprecipitation/Western blot analysis. A post-treatment tumor biopsy should be collected between Cycle 1 Day 22 and Cycle 2 Day 1 at least 1 hour post-dose. In subjects who have been on treatment  $\geq 8$  weeks and with the subject's agreement, additional post-treatment biopsies may be collected.

Blood samples (pre-dose) will be collected during Treatment Period 1 on Day 1, Day 2, Day 3, and Day 4 (Cohorts 1-4), and during Treatment Period 2 Cycle 1 (Cohort 5 and all subsequent Dose Escalation cohorts) on Day 1, Day 8, Day 15, and Day 22, and on Day 1 of Cycles 2-5 for evaluations of pharmacodynamic changes of factors including phosphate, glucose, FGF 19, 21, and/or 23 utilizing standard blood chemistry methodologies and ELISA-based assays.

For subjects enrolled in the Expanded Cohort, blood samples for evaluations of pharmacodynamic changes of FGF 19, 21, and 23 will be collected on Day 1 of the first six cycles.

Samples for pharmacokinetic and pharmacodynamic assessments will be labeled by personnel from the institution with subjects' study ID; subjects' identity will not be made known to employees from the Sponsor, additional collaborators, or other investigators. Samples will only be used for the purposes of the protocol and will only be used by ArQule's personnel or by an external laboratory chosen by ArQule to outsource the analyses according to internal guidelines. Samples will be kept until all protocol-related analyses are completed, for a period not exceeding 10 years or as required by local law.

Detailed instructions for collection, testing, and shipment of tissue, plasma, or serum pharmacodynamic samples will be provided in the laboratory manual.

## 6.7 Tumor Evaluation

Tumor assessments (CT scan, PET scan, or MRI) will be performed at Baseline, and every eight weeks (e.g., on Day 1 of every odd cycle, Day 1 Cycle 3, Day 1 Cycle 5, or Week 8, Week 16, etc.) or as otherwise clinically indicated.

For subjects who do not experience disease progression and continue to benefit from the treatment after 11 cycles, tumor evaluation may be performed every 3 months (e.g., Day 1 of Cycle 14, Day 1 of Cycle 17, Day 1 of Cycle 20, etc.) upon agreement between the Investigator and ArQule's Medical Monitor.

Standard imaging studies should be performed according to institutional procedures and/or standard of care. Tumor response will be evaluated using relevant guidelines (see Appendix 6 for RECIST 1.1 guidelines).

## 6.8 Tumor Biopsy

All enrolled subjects should agree to provide archival tissue and to have a fresh tumor biopsy.

- For ALL subjects, archival tissue biopsy samples should be collected
- For subjects enrolled into the Expanded Cohort, samples will be tested for genetic alterations, that may include FGFR genetic alterations, FGFR gene fusions, and KIT/PDGFR mutations
- For subjects enrolled in the Dose Escalation and Food-effect Cohorts, samples will be tested to assess protein expression levels of FGFR family members (FGFR1 and FGFR2) and/or to confirm the tumor's genomic profile, e.g., KIT/PDGFR mutation or *FGFR1-3* amplification, mutations/gene rearrangement (fusion, translocation) status
- If archival samples are not available, a fresh core needle biopsy or fine needle aspiration (FNA) may be collected during the Screening Period. Core needle biopsy samples collected within 30 days prior to the first dose of ARQ 087 are considered fresh.
- If allocated slots are available, for subjects eligible for enrollment in the Dose Escalation cohorts, paired (pre- and post-treatment) tumor biopsy is optional. The paired tumor biopsy will be done only if, in the Investigator's opinion, a minimally invasive biopsy may be performed.
- For all subjects enrolled in the Food-effect Cohort, a paired tumor biopsy is mandatory.
- In Cohorts 1-4, tumor samples will be collected at Baseline/archival and 4-6 hours after ARQ 087 administration on Day 1 of Treatment Period 1 or on Day 1 of Cycle 1 of Treatment Period 2. Starting with Cohort 5, a post-treatment tumor biopsy should be collected between Cycle 1 Day 22 and Cycle 2 Day 1 at least 1 hour post-dose. (Additionally, optional post-treatment biopsies may be collected at any time during treatment at least 1 hour post-dose.)
- For subjects enrolled in the Expanded Cohort pre- and post-treatment (paired) biopsy is optional. If a paired biopsy is deemed safe and with the subject's consent, the biopsy may be performed at Baseline, at any time point between Cycle 1 Day 22 and Cycle 2

Day 1 visits, and an additional optional biopsy may be performed at any time during the treatment including the End of Treatment Visit.

Prior to a subject's enrollment, the Investigator should establish availability of suitable pathology specimens and/or evaluate the subject's eligibility for tumor biopsy.

The testing may include assessment of FGFR1 and FGFR2 protein levels, pFGFR, pFRS2 $\alpha$ , and pERK expression levels.

Fresh tumor biopsy samples must be frozen immediately after the samples are obtained. Detailed instructions for collection, shipment, and testing of tissue samples will be provided in the laboratory manual.

## 7 TREATMENT

### 7.1 ARQ 087

ARQ 087 capsules (multiple strengths of 25 mg and 100 mg) will be supplied to the research pharmacy at the clinical site. Study drug will be labeled as an investigational agent according to relevant Federal laws and regulatory guidelines.

#### 7.1.1 Investigational Product Accountability

ArQule will provide study drug and drug accountability documentation required for completion of this study. The recipient will acknowledge receipt of the drug indicating shipment content and condition. Damaged supplies will be replaced.

Drug Accountability Records (logs) will be maintained. These records should record quantities of study drug received and quantities dispensed to subjects, including lot number, date dispensed, subject identifier number, subject initials, protocol number, dose, quantity returned, balance remaining, and the initials of the person dispensing the drug. Accurate records of all study drug dispensed from and returned to the study site are to be maintained. The study site must supply a copy of their drug destruction policy to ArQule before authorization for destruction will be granted. Product accountability will be monitored throughout the study. Upon completion or termination of the study, and after inventory by an ArQule monitor or designated representative, all unopened drug is to be returned to ArQule or designee in the original containers.

#### 7.1.2 Storage and Handling

At a study site, ARQ 087 should be stored refrigerated (2°-8°C; 35°-46°F) or at controlled room temperature (15°-30°C; 59°-86°F) depending on the storage instructions provided on the label of the container in which the capsules are shipped to the site and dispensed to the subject. Until dispensed to the subject, the study drug should be stored in a secure locked area accessible to authorized personnel only.

#### 7.1.3 ARQ 087 Administration

ARQ 087 will be administered once a day, orally. ARQ 087 must be administered in the fasted state, except for subjects who are enrolled in the Food-effect Cohort. Subjects in the Food-effect Cohort will be asked to take ARQ 087 with their morning meals and to keep a food diary (breakfast).

For administrative reasons, during continuous dosing, the treatment period is divided into 4-week cycles (28 days).

The dose of ARQ 087 to be administered depends on the dose level cohort to which the subject is enrolled, with the initial dose level of 25 mg qod, see Section 4.1 for details.

For individual subjects, treatment will continue until unacceptable toxicity, disease progression (clinical or radiological), or other discontinuation criterion is met. It is expected that most subjects will receive ARQ 087 for one to six treatment cycles (4 to 24 weeks).

## 7.2 Missed or Vomited Doses

A missed or vomited dose should not be replaced. The subject should be instructed to take the next scheduled dose at the regularly scheduled time. If the subject vomited the very first dose of study drug, the subject may be re-challenged per discretion of the Investigator.

## 7.3 Dose Modifications

In general, once the dose of ARQ 087 has been modified for a subject, all subsequent cycles should be administered to that subject at the modified dose. The modified dose will be considered the maximum dose for all subsequent cycles for that subject.

When a drug-related toxicity is observed, dose delays and/or reductions in ARQ 087 administration are allowed. If dose reduction is indicated, a subject should be assigned to the previous (lower) cohort dose (dose re-escalation is not permitted). In the event of a dose modification, the dose change(s) must be captured in the electronic data capture (EDC) system. If questions or considerations regarding dose modification arise or a specific dose modification is needed, ArQule's Medical Monitor or designee should be consulted.

If the subject experienced a DLT, such subject should be permanently discontinued from the treatment. During the dose escalation period, intra-subject dose escalation is not allowed. Once the MTD/RP2D is reached, intra-subject dose escalation may be considered to optimize the dose level taking into consideration the available dosage strengths. A maximum of one intra-subject dose escalation per subject may be considered.

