**Table 4.1 Dosing Guidelines**

Cohort	Total Daily Dose a	Dose per Administration	Number of Subjects
Dose Escalation Cohorts: Part 1			
	25 mg	1 cap x 25 mg x twice a week	3-6 b
1 a	25 mg	1 cap x 25 mg x qod	3-6 b
2	25 mg	1 cap x 25 mg x qd	3-6 b
3	50 mg	2 caps x 25 mg x qd	3-6 b
4	100 mg	1 caps x 100 mg x qd	3-6 b
5*	150 mg	2 caps x 25 mg & 1cap x 100 mg x qd	3-6 b
6	200 mg	2 caps x 100 mg x qd	3-6 b
7	250 mg	2 caps x 25 mg & 2 caps x 100 mg x qd	3-6 b
8	325 mg	1 cap x 25 mg & 3 caps x 100 mg x qd	3-6 b
9	425 mg	1 cap x 25 mg & 4 caps x 100 mg x qd	3-6 b
10	550 mg	2 caps x 25 mg & 5 caps x 100 mg x qd	3-6 b
Food-effect a	400 mg	4 caps x 100 mg qd	at least 6
Expanded Cohort: Part 2			
Expanded e	300 mg	3 caps x 100 mg x qd under fasting conditions	approx. 50-60

\*Starting from Cohort 5, the dose escalation will follow a modified Fibonacci scheme (increase by 50%,

30%, and 25%)

To avoid potential non-compliance due to capsule burden, the dose escalation may be stopped at the dose level of 550 mg/daily

[figure not shown]
aTotal daily dose must be administered one hour prior to or two hours after the meal [Exceptions: 1) Cohort 1 is dosed every other day and 2) Food-effect Cohort]

bIf a DLT is seen in one of three treated subjects, an additional three subjects will be treated at the same dose level

cBased on the safety profile and PK results of the Food-effect cohort, the dose of 300 mg qd under fasting conditions has been defined as MTD/RP2D and should be further evaluated in the Expanded Cohort

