#### 4.5 Dose-Limiting Toxicity

Dose-limiting toxicities will be determined during the first four weeks/28 days (first cycle) of Treatment Period 2 (Cohorts 1-4) or during Cycle 1 (Cohort 5 and all subsequent cohorts). A DLT is defined by the occurrence of any of the following toxicities related to ARQ 087 within the first 28 days of continuous treatment (Treatment Period 2 or Cycle 1 of Continuous Dosing) and graded according to the Common Terminology Criteria for Adverse Events (CTCAE) version 4.03:

- Grade 4 anemia
- Grade 4 neutropenia
- Grade 4 thrombocytopenia
- Grade 3 neutropenia with fever ( $\geq 38^{\circ}\text{C}/100.4^{\circ}\text{F}$ )
- Grade 3 neutropenia lasting longer than 7 days despite optimal treatment
- Grade 3 thrombocytopenia in the presence of bleeding
- $\geq$  Grade 3 hyperglycemia (fasting blood glucose  $> 250$  mg/dL or non-fasting  $> 500$  mg/dL) requiring insulin (uncontrolled with metformin)
- $\geq$  Grade 3 non-hematological toxicity of any duration, except for the following:
  - Nausea, vomiting, or diarrhea responding to optimal medical management within 48 hours
  - Alopecia
- Any other toxicity that in the view of the Investigator represents a clinically significant hazard to the subject

**Note:** During the dose escalation phase, if the subject experienced a DLT, such subject should be permanently discontinued from the treatment.

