**Table 7.1 Dose Delays/Reductions for Drug-Related Toxicity**

Event Grade	Action
Grade 1 or 2, including significant increase in LFTs (as assessed by the Investigator) and alopecia	Continue current dose level, unless dose interruption/modification may be clinically indicated, e.g., due to significant increase in LFTs
Grade 3-4 nausea, vomiting or diarrhea lasting < 24 hours	Withhold ARQ 087 until recovery to Grade 1 or baseline. If recovery occurs within 24 hours, restart ARQ 087 at the current dose level.
Grade 3-4 toxicity, including nausea, vomiting or diarrhea lasting $\geq$ 24 hours	
Withhold ARQ 087 until recovery to Grade 1 or baseline.
 
 
- If recovery occurs within 14 days, restart ARQ 087 at the dose and schedule of the previous cohort for all subsequent cycles, unless further dose reduction is required.
 
- If recovery occurs within 21 days of the drug hold, ARQ 087 may be restarted upon agreement between the Investigator and the Sponsor's Medical Monitor. Treatment should be restarted at the dose and schedule of the previous cohort for all subsequent cycles, unless further dose reduction is required.
 
- If recovery occurs after more than 21 days of the drug hold, ARQ 087 should be permanently discontinued
 

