**Table 7.2 ARQ 087 Dose Reduction Schema**

Current Dose	Dose after Reduction
Dose Level 1: 3 capsules qd (300 mg daily)	Dose Level 2: 2 capsules qd (200 mg daily)
Dose Level 2: 2 capsules qd (200 mg daily)	Dose Level 3: 1 capsule qd (100 mg daily)
Dose Level 3: 1 capsule qd (100 mg daily)	

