5 STATISTICAL METHODS AND DATA ANALYSIS

5.1 Determination of Sample Size

No formal statistical tests of hypotheses will be performed in this study. The exact number of subjects estimated for this study depends on the number of cohorts investigated based on the toxicity encountered. It is expected that approximately 60-120 subjects will be enrolled in this study.

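### For a subject at 300 mg, Protocol Section 7.3 and Table 7.1 lead to a different reduced dose from Table 7.2, and the scope of the DLT stop is stated inconsistently

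*Protocol*

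**What the plan says.** **Reduced dose.** Section 7.3 of the Protocol gives the general rule: "a subject should be assigned to the previous (lower) cohort dose (dose re-escalation is not permitted". Table 7.1 applies the same idea to Grade 3-4 drug-related toxicity. If recovery occurs within 14 days, the site is to "restart ARQ 087 at the dose and schedule of the previous cohort for all subsequent cycles". If it occurs within 21 days, restart at that reduced level needs the Medical Monitor's agreement. After more than 21 days the drug is stopped. Neither Section 7.3 nor Table 7.1 confines this rule to Part 1.

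Table 4.1 lists Cohort 7 at 250 mg, made up as "2 caps x 25 mg & 2 caps x 100 mg x qd", the Food-effect Cohort at 400 mg and the Expanded Cohort at 300 mg. Table 7.2 starts at 300 mg, gives the first reduced level as "Dose Level 2: 2 capsules qd (200 mg daily", and then goes to 100 mg. It is not labelled for either part of the study, and neither the text of Section 7.3 nor Table 7.1 refers to it.

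**DLT stop.** Section 7.3 states: "If the subject experienced a DLT, such subject should be permanently discontinued from the treatment". Section 4.5 states: "During the dose escalation phase, if the subject experienced a DLT, such subject should be permanently discontinued from the treatment". The Synopsis carries the same escalation-phase limit and labels its DLT criteria as Part 1. Section 4.5 also sets the DLT window for Cohort 5 and every later cohort, without saying whether the Expanded Cohort is one of them. Table 7.1 does not mention DLTs.

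**The concern.** These are operative dosing instructions, and two of them give different answers for a subject at the recommended Phase 2 dose. A site that reads Section 7.3 or Table 7.1 and looks up the lower cohort reaches one dose; a site that reads Table 7.2 reaches another. Safety and tolerability is the primary objective and further evaluation of the 300 mg dose is a secondary one, so the management of toxicity at that dose should not depend on which passage a site happened to read.

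The unlimited DLT sentence raises a related question: whether a qualifying toxicity ends treatment or permits a restart at a lower dose. SAP Section 5.4.7 counts events leading to discontinuation separately from those leading to interruption followed by dose reduction, so the passage followed can decide which count a subject enters. A stop in Cycle 1 can also keep a subject out of the evaluable population, which requires at least one cycle of treatment (SAP Section 4.4).

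**Working it through.** The plan has no figure to reproduce, and the SAP says that "No formal statistical tests of hypotheses will be performed in this study". The check is a lookup, followed by a comparison of scope.

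**Step 1: inputs.** Daily doses in Table 4.1, Cohorts 1 to 10: 25 mg every other day, then 25, 50, 100, 150, 200, 250, 325, 425 and 550 mg once daily; Food-effect 400 mg; Expanded 300 mg. Table 7.2: 300 to 200 mg, then 200 to 100 mg.

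**Step 2: what the previous lower cohort means at 300 mg.** The Expanded Cohort has no number. The row directly before it is the Food-effect Cohort at 400 mg, which is not lower, so the row-order reading fails. The highest cohort dose below 300 mg is 250 mg (Cohort 7).

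**Step 3: size.** Reduction = (current dose − reduced dose) / current dose.

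| Current dose | Previous lower cohort (Table 4.1 lookup) | Table 7.2 |
|---|---|---|
| 300 mg | 250 mg: (300 − 250)/300 = 16.7% | 200 mg: (300 − 200)/300 = 33.3% |
| 200 mg | 150 mg: (200 − 150)/200 = 25% | 100 mg: (200 − 100)/200 = 50% |

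The two instructions differ by 50 mg/day at each of these steps. A subject reduced to 250 mg is also at a dose that Table 7.2 does not list, so that table gives no next step.

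**Step 4: scope of the DLT stop.**

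| Place | Scope |
|---|---|
| Section 7.3 | No limit stated; the next sentence of the same paragraph does carry an escalation-period limit, on a different matter |
| Section 4.5, note | Dose escalation phase |
| Synopsis, dose-escalation criteria | Dose escalation phase |
| Synopsis, DLT criteria | Labelled Part 1 |
| Section 4.5, DLT window | Cohort 5 and every later cohort |
| Table 7.1 | No DLT exception |

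**Step 5: where stop and restart could collide.** The event must meet a DLT criterion, for example a related non-hematological toxicity of Grade 3 or higher in the first 28 days, outside the listed exceptions. It must also recover within 21 days. For such an event the unlimited sentence in Section 7.3 says stop, and Table 7.1 says restart (within 14 days) or possible restart (within 21 days). Beyond 21 days both say stop. In Part 1, the Synopsis, Section 4.5 and Section 7.3 agree on stopping, and Table 7.1 only lacks a stated exception. In Part 2 there is a collision only if the Section 7.3 sentence is read without the limit stated elsewhere.

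**The case against.** The strongest reply on the reduced dose is that the specific rule overrides the general one. Table 7.2 starts at 300 mg, a dose that Table 4.1 gives only to the Expanded Cohort, and a site with a 300 mg subject finds an explicit row for it. The 250 mg figure is printed nowhere as a reduced dose. Section 7.3 also directs sites to the Medical Monitor if a question arises or a specific modification is needed, and dose changes must be recorded in the data capture system. All of this stands, and it makes divergence a possibility rather than a certainty. It does not remove the conflict: no sentence makes Table 7.2 the Part 2 rule, both capsule strengths needed for 250 mg are supplied (Section 7.1), and a site that reads only one passage has no reason to ask.

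On DLTs, a reader might infer that the same Cycle 1 Grade 3 event in Part 2 is simply a stop in one place and a restart in another. The documents do not support that. The Synopsis and Section 4.5 limit the stop to dose escalation, and the Synopsis labels the DLT criteria Part 1. Many Grade 3 events are not DLTs under the listed criteria: neutropenia without fever lasting 7 days or less, thrombocytopenia without bleeding, anemia, and nausea, vomiting or diarrhea that responds within 48 hours. What remains is a question of scope. It is not fully settled, because the Section 4.5 window covers every cohort after Cohort 5, the Synopsis elsewhere counts the Expanded Cohort among the cohorts from Cohort 5 onward, and the SAP tabulates DLT events in summaries that include the Expanded Cohort.

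A reader might also infer a known distortion of exposure or response at 300 mg. That is not shown either. Section 4.1.1 reports Day 22 exposure essentially unchanged from 250 to 425 mg, so nominal dose differences cannot be translated directly into exposure. SAP Section 5.4.5 also analyzes response in the safety population, which does not depend on completing a cycle.

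**Conclusion.** The point holds as an internal inconsistency in the dose-modification text. For a subject at 300 mg the instructions yield 250 mg or 200 mg, a nominal reduction of 16.7% or 33.3%, with a second mismatch at 200 mg. This rests on one assumption: that the previous lower cohort means the nearest lower dose in Table 4.1.

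The DLT point is narrower. The unlimited sentence in Section 7.3 does not match the escalation-phase limit in the Synopsis and Section 4.5, and Table 7.1 mentions no exception. It does not establish that Part 2 subjects face contradictory rules.

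The planned 50-60 Expanded Cohort subjects are the population at risk, not the number affected. The documents do not say how many would need a reduction, and sites could differ rather than would. Because the text concerns patient safety and is cheap to correct, it should be corrected. No view is taken on which dose or which stopping rule is right.

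**What to change.** Reconcile Table 4.1, Section 7.3, Table 7.1 and Table 7.2 by stating which reduction instruction governs each part of the study, and label Table 7.2 accordingly. Where the cohort-based wording is meant to apply, say what it refers to for a subject in the Expanded Cohort, which has no number.

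Separately, give the DLT discontinuation rule one scope across the Synopsis, Section 4.5, Section 7.3 and Table 7.1, and state whether the DLT window in Section 4.5 includes the Expanded Cohort.

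The clinical choices are for the sponsor. The cost is a wording change in the protocol or a clarification letter to sites; the planned sample size and analyses do not change.
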